# LIST OF ABBREVIATIONS (Examples)

SID	Study Identification
KUMC	University of Kansas Medical Center
U	Urine
S	Serum
Т	Tissue
Μ	Month
HSC#	Human Subjects Committee #
USSQ	Ureteral Stent Symptom Questionnaire

# **1.0 STUDY SUMMARY**

# **1.1 AIM AND HYPOTHESIS**

The objective of this project is to compare the efficacy of hyoscyamine to tamsulosin monotherapy in treating lower urinary tract symptoms in patients with indwelling double-J ureteral stents.

Ureteral stents are routinely used in a variety of urologic conditions. Unfortunately, indwelling ureteral stents commonly cause significant pain and discomfort due to irritation to the urinary system. Many studies have looked at methods to reduce these uncomfortable symptoms ranging from altering stent designs to pharmacologic therapies attempting to alleviate stent-discomfort. However, stent-related discomfort continues to be an issue and is often the cause of their removal earlier than planned. While the efficacy of certain alpha blockers and anticholinergics in treating stent-related symptoms have been studied, the data for the use of hyoscyamine in this setting is lacking. A literature search yielded no studies evaluating the use of hyoscyamine in this setting to date. We hypothesize that hyoscyamine (brand name Levsin) is equivalent to tamsulosin in treating lower urinary tract symptoms in patients with indwelling double-J ureteral stents due to its anticholinergic properties. Furthermore, we hypothesize that patients in the hyoscyamine arm will not require additional pain medications (e.g. Pyridium, narcotics) to help control stent-related discomfort compared to the tamsulosin arm.

# BACKGROUND AND RATIONALE

# **2.1 DISEASE BACKGROUND**

Ureteral double-J stent was first described by Finney et al in 1978, and has since become a routine and indispensable urological tool used in a variety of conditions including obstructing kidney stones, obstructing ureteral or bladder masses, injury or trauma to the ureter or kidney, scarring in the ureter, or for masses in the pelvis that extrinsically compress the ureter. Despite the usefulness of ureteral stents, patients experience uncomfortable stent-related symptoms including bladder spasms, pain, frequency, urgency, and as a result, an overall decrease in quality of life. Studies investigating the etiology of these symptoms found that the important factors contributing to stent discomfort include the pressure transmitted to the renal pelvis during urination, irritation to the trigone caused by the intravesicular curl of the stent, and spasms of ureteral smooth muscle due to the presence of a indwelling foreign object. One study showed 80% of patients had stent related discomfort that interfered with their daily activities, which resulted in 32% of patients requesting the stent removed prematurely. Many studies have

looked at improving these uncomfortable symptoms including using stents with tapering tails at the distal end, various stent coatings including Hydrogel and carbon, and pharmacological treatments with alpha blockers, anticholinergics and empirically prescribed analgesics.

# **2.2 RATIONALE**

Providers routinely prescribe alpha antagonists and/or anticholinergics to patients in order to relax the bladder and minimize the discomfort. Numerous studies have investigated the beneficial effect of alpha antagonists for ureteral stent-related discomfort. Tamsulosin is a selective  $\alpha_{1a}$ -blocker that antagonizes  $\alpha_1$  mediated contraction of prostate, bladder and proximal urethral smooth muscle. Owing to this mechanism, it reduces urethral and bladder outlet resistance and decreases urinary reflux, ureteric motility and bladder hyperactivity, all of which work to alleviate stent-related discomfort. Similarly, many studies have evaluated the utility of anticholinergics in treating stent discomfort since many of the stent-related symptoms are similar to overactive bladder symptoms caused by muscarinic receptor mediated involuntary bladder contractions. Hyoscyamine is a prescription drug that became available before 1938 and is considered a 'Grandfather Drug.' Hyoscyamine is one of the least expensive anticholinergics on the market, and furthermore, it has more favorable pharmacokinetics compared to other anticholinergics that are typically prescribed for stent-related discomfort. Oxybutynin, for example, has an onset of action of 30 minutes to 1 hour with time to peak effect of 3 to 6 hours, compared to Hyoscyamine which has an onset of action of 2-3 minutes with time to peak effect of 30 minutes to 1 hour. Since stent-related discomfort can be aggravated with activity and typically presents in a waxing and waning fashion, the rapid acting therapeutic effects of hyoscyamine may provide tremendous relief for patients with indwelling stents. A review of literature in PubMed did not yield any studies evaluating the efficacy of hyoscyamine in the treatment of stent-related discomfort. Since we routinely use hyoscyamine to treat patients with ureteral stent discomfort, it would be interesting to know how effective hyoscyamine is when used in this setting. Given the well-published data on tamsulosin, we would like to conduct a formal study comparing the efficacy of hyoscyamine to tamsulosin for treating symptoms associated with ureteral stents as assessed by a validated questionnaire, the Ureteral Stent Symptom Questionnaire, and provide the first research-based evidence regarding the efficacy of hyoscyamine for the treatment of stent-related discomfort.

# **3.0 STUDY OBJECTIVES**

# **3.1 PRIMARY OBJECTIVE**

To evaluate the efficacy of hyoscyamine compared to tamsulosin in improving the lower urinary tract symptoms of patients with indwelling double-J ureteral stents as assessed by the validated Ureteral Stent Symptom Questionnaire (USSQ).

# **3.2 SECONDARY OBJECTIVE**

To determine if there is a difference between the amount of additional medications needed to treat stent related discomfort between patients receiving hyoscyamine versus those that receive tamsulosin.

To determine factors contributing to patients needing additional medication for treatment of stent-related discomfort.

# 4.0 PATIENT ELIGIBILITY

# 4.1 INCLUSION CRITERIA

- 1. Patients must be 18 years of age or older
- 2. Patient must require placement of a ureteral stent(s), per standard of care, following routine urological procedures including, but not limited to, ureteroscopy, stone extraction, or management of upper tract transitional cell carcinoma
- 3. Patient must agree to abstain from other clinical studies during the study period

# 4.2 EXCLUSION CRITERIA

- 1. Patients younger than 18 years of age
- 2. Patients with chronic or pre-existing indwelling stents
- 3. Patients currently receiving anticholinergic or alpha blocker therapy
- 4. Patients with chronic opioid or analgesic usage
- 5. Patients with chronic pain syndrome or symptomatic benign prostatic hyperplasia
- 6. Patients with an active untreated urinary tract infection
- 7. Patients who are currently pregnant or nursing
- 8. Patients with allergies or contraindication to either tamsulosin or hyoscyamine
- 9. Patients on active chemotherapy
- 10. Patients currently receiving other investigational therapy
- 11. Patients who are unable to sign consent/answer questionnaire due to compromised mental capacity or language barrier (the questionnaire is not validated in other languages)
- 12. Patients who have a stent placed emergently for an obstructing stone or septic stone without immediate stone removal,

13. Any stents placed that will stay in for longer than 2 weeks, including patients who suffered a ureteral injury (Grade 2 or above) during the procedure that will be classified as a screen fail

# 4.3 WITHDRAWL/TERMINATION CRITERIA

Patients who do not undergo the placement of a ureteral stent following a routine urological procedure will be withdrawn from the study. If the patient was scheduled to undergo the stent placement and for any reason the plan changed or was cancelled that patient will be taken off the protocol and considered discontinued. The patient spot will be replaced and the study ID number will not be reused. This will allow the protocol to be completed once 94 patients have completed treatment based on statistical calculations from the Biostatistics department (below).

Patients will be allowed to withdraw from the study at any time. If a patient cancels permission to use their health information the research team will stop collecting any additional information about them moving forward. The research team may use and share information that was gathered before they received the patient's withdrawal. The entire study may be discontinued for any reasons without the patients consent by the investigator conducting the study.

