# **5.3 STUDY PROCEDURES**

To assess ureteral stent symptoms, we will be conducting the Ureteric Stent Symptoms Questionnaire (USSQ). The USSQ was created by Joshi et al as an instrument to measure stentrelated morbidity. The USSQ has been validated as a reliable instrument to measure the impact of ureteral stents. This validated questionnaire has been used in many previous studies regarding stent pain. In our study, the USSQ will be conducted prior to stent placement, on POD1, POD7 (or just prior to the time of stent removal if the removal occurs prior to day 7), and POD30. Basic demographic information, stent duration, stent size, stone location/size and obstructing vs. non-obstructing (if applicable), post stent insertion complications, drug diary information and questionnaire responses will be entered into a REDCap database for storage and analysis. The stent diameter will be 6Fr for all patients in the study. The appropriate stent length will be assigned to the patient based on cross sectional imaging. If cross sectional imaging is not available then stent length with be measured using a open-ended catheter to measure ureteral length. A small portion of these patients will be seen in the emergency department or while they are having an acute pain episode, so we expect that some of the pre-stenting questionnaires may not provide an accurate baseline for symptoms in these patients, hence the POD30 questionnaire will be obtained.

After informed consent is obtained, the patient will be prospectively randomized to either treatment arm in an open-label fashion using REDCap's randomization function to determine which therapy they will receive after stent placement. In the event that a patient does not find relief with their particular treatment arm, they will be permitted to receive additional narcotics or Pyridium. Should the patient continue to have unrelieved symptoms, treatment crossover is allowed since the study is designed in an intent-to-treat fashion.

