Questionnaires will be completed either in person if patient is in clinic or inpatient, or via a REDCap survey prior to stent placement, POD1, POD7 or at the time of stent removal if the removal occurs prior to day 7, and POD30. Patients with strings attach to stents will be included as there is no literature to suggest that strings cause additional stent irritation. Both medications will be stopped once the ureteral stent is removed as part of routine urological follow-up care for the primary etiology. Once the number of study participants reaches the pre-determined goal as calculated by our biostatistician, study enrollment will conclude and we will begin analyzing the data.

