# 5.4 STUDY DESIGN AND SAMPLE SIZE

Total sample size: 100

The study will be conducted as a randomized comparative effectiveness trial with two arms. Subjects will be randomized to one of two treatments WITH either hyoscyamine or tamsulosin. Our hypothesis is that the hyoscyamine is at least as effective as tamsulosin in treating lower urinary tract symptoms. Symptoms will be quantified using the Urinary Symptom Index (USI) of the validated Ureteral Stent Symptom Questionnaire (USSQ). To address the hypothesis, the study will be conducted as a non-inferiority trial, following the hypothesis that hyoscyamine is not inferior to tamsulosin by more than a 15% margin in terms of the USI. The sample size was estimated using the PowerTOST package for the R statistical environment, based on a nominal power of 80% and an alpha-level of .025 for the one-sided t-test. Our null hypothesis is therefore that the mean USI for those treated with tamsulosin is more than 15% greater than those treated with hyoscyamine, so that by rejecting it, we may conclude hyoscyamine is not-inferior to tamsulosin by more than a 15% margin of USI for treating lower urinary tract symptoms. Furthermore, we assume that the coefficient of variation (CV) for the mean Urinary Index Score

will be similar to that in Park, et al.20 The CV in that study for the Urinary Symptom Index at week 2 after stent placement for the tamsulosin group was approximately .25. This is slightly higher, but similar to the CV of .22 for the USI in Maldonado-Avila, et al. which collected data at week 1, and therefore should be slightly conservative.21 Using these assumptions, we estimated that the sample size for each arm would need to be approximately 47, in order to have the desired power.

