# **5.5 DATA ANALYSIS**

The main hypothesis of the non-inferiority of hyoscyamine to tamsulosin for treating lower urinary tract symptoms will be tested using a t-test for non-inferiority of the change in USI between POD1 and POD7 (or day of stent removal if removed before day 7) in each treatment arm. This should be slightly more powerful than the t-test at POD7 alone that we used to estimate the sample size, but there are not enough data available for the distribution at POD1 in order to make a good estimate of the change. The non-inferiority margin will be 15% of the change in USI. The primary analysis will be conducted as intention-to-treat (ITT). That is, subjects will be analyzed as belonging to the arm they were randomized to, irrespective of later crossover or other modifications. This approach is in line with the current statement on Consolidated Standards of Reporting Trials (CONSORT). Descriptive statistics will be used to describe the results from all USSQ domains at each timepoint (i.e. mean and standard deviation, along with confidence intervals for urinary symptom index, pain symptom index, etc.). We will also conduct non-inferiority tests of change in score for ITT with hyoscyamine versus tamsulosin for the other domains spanned by the USSQ, including pain symptom index, general health index, work performance index, and sexual matters between POD1 and POD7, although we may not be wellpowered to detect non-inferiority for these additional domains.

The secondary goal of determining if there are differences in the amount of additional medications need to treat stent-related discomfort between treatment arms will be examined primarily through descriptive statistics. The drug diaries of all subjects will be used to tabulate the kinds and amounts of additional medications used. For each subject, the number of days that additional medications were used will be counted. The proportion of days that additional medications were used will be calculated for each group and 95% confidence intervals will be calculated.

Finally, we will also calculate the informed consent rate, and the discontinuation rate for those patients needing to be removed from the study in each arm.

In all cases, a p-value  $\leq$  .05 will be taken as a statistically significant result.

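### The primary analysis is labelled ITT, but a t-test of the POD1-to-POD7 change uses only patients with both scores, and the plan has no missing-score method or sensitivity analysis

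*Combined protocol and SAP*

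**What the plan says.** **Primary test.** In Section 5.5 the main hypothesis "will be tested using a t-test for non-inferiority of the change in USI between POD1 and POD7", with the day of stent removal standing in for POD7 when removal is earlier. The same section labels the analysis ITT and defines that as keeping each patient in the randomised arm whatever happens later, crossover included.

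**Closing the study.** Section 4.3 says "This will allow the protocol to be completed once 94 patients have completed treatment". Section 5.4 gives "Total sample size: 100" and about 47 per arm. Section 5.3 stops enrolment on a count of participants: "Once the number of study participants reaches the pre-determined goal as calculated by our biostatistician".

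**Losses.** Randomisation precedes stenting: "After informed consent is obtained, the patient will be prospectively randomized to either treatment arm in an open-label fashion" (Section 5.3; the schedule in 5.6 places it at enrolment). A patient whose stent placement is changed or cancelled is discontinued under Section 4.3, and "The patient spot will be replaced and the study ID number will not be reused". Under exclusion 13 in Section 4.2, a patient with a Grade 2 or worse ureteral injury during the procedure becomes a screen failure. Patients may withdraw at any time. If permission to use health information is cancelled, "the research team will stop collecting any additional information about them moving forward", although data already gathered may be used (4.3).

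**Missing scores.** No section says what happens when a POD1 or POD7 score is absent. Section 5.5 promises a discontinuation rate per arm, but no analysis set, imputation, model or sensitivity analysis.

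**The concern.** The ITT definition in 5.5 settles which arm a patient is counted in. It does not settle whether the patient is counted at all, and the named test leaves out any randomised patient without both scores.

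This matters more than usual here. The trial succeeds by failing to find hyoscyamine worse by more than the margin, so anything that removes badly relieved hyoscyamine patients makes success easier. Patients know their treatment, and one regimen is as-needed while the other is daily, with different side effects. Unequal loss between arms is therefore plausible. The result would carry an ITT label with nothing planned to show how far it depends on the missing scores.

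**Working it through.** **1. What 94 stands for.** Inputs from Section 5.4: margin 15%, CV .25, one-sided alpha .025, power 80%. The true difference is not stated; assume 0. On the raw scale, as fractions of the mean, a noncentral-t calculation gives 45 per arm and power of 82.1% at 47 per arm. That is close to the plan's figure of about 47. The PowerTOST scale is not given; log-scale versions give 38 to 50 depending on which side the margin is set. So 2 × 47 = 94 is the number of patients needed with usable data, with no allowance for loss.

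**2. What 100 allows.** 1 − 94/100 = 6% loss. Using 94/(1 − d), the number to randomise would be 105 at 10% loss, 111 at 15% and 118 at 20%. If 100 are randomised and only complete pairs are used, power on this scale is 80.4% at 10% loss (45 per arm) and 75.5% at 20% (40 per arm).

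**3. Who is left out.** By Sections 5.3, 5.5 and 5.6:

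| Patient | In the t-test? |
|---|---|
| Crosses over or takes additional medication, both scores present | Yes, in randomised arm |
| Stops study drug, both scores present | Yes, in randomised arm |
| Stent removed before day 7, USSQ done that day | Yes |
| Misses POD1 or POD7, or withdraws before POD7 | No |
| Randomised but not stented, or made a screen failure | No; removed after randomisation |

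**4. Size of a possible bias (illustration).** Let d be the fraction missing in an arm, and g the number of SDs by which the missing patients are worse than the observed ones in that arm. The observed mean then looks better than the whole-arm mean by d × g × SD. With equal g in both arms:

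- bias toward non-inferiority = (d for hyoscyamine − d for tamsulosin) × g × .25
- standard error with 47 complete pairs per arm = .25 × √(2/47) = .0516
- one-sided type I error with the true difference at the margin = Φ(−1.96 + bias/.0516)

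| Loss (hyoscyamine / tamsulosin) | g = 0.5 | g = 1 |
|---|---|---|
| 10% / 0% | bias .0125, error 4.3% | bias .025, error 7.0% |
| 10% / 10% | 2.5% | 2.5% |
| 15% / 5% | 4.3% | 6.9% |
| 20% / 5% | 5.5% | 10.7% |
| 5% / 15% | 1.4% | 0.7% |

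The first row uses the normal formula and the others a noncentral t; the two agree to within 0.1 point. A bias of .025 is one sixth of the .15 margin.

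**5. Limits of step 4.** The loss rates and g are assumed. The SD is that of the USI level, with the margin a fixed 15% of the mean. Section 5.5 tests the change, with a margin of 15% of the change, and says the POD1 data are too few to estimate the change well. The effect on a change score also depends on the lost patients' POD1 values, for which the documents give nothing.

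**The case against.** The case on the other side is substantial.

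- A reader might infer from the 94-completer rule that the analysis is restricted to patients who completed treatment. It is not. Completing treatment appears in 4.3 as a rule for ending the study, not as an analysis set, and nothing in 5.5 excludes a patient for stopping the drug.
- A reader might also infer that the plan removes the patients who do worst. The plan in fact works to keep them: crossover stays in the randomised arm, and early stent removal triggers the questionnaire that day. The explicit replacement rule covers patients who never received a stent, who are not poor responders. Remote questionnaires may help completion as easily as hinder it.
- The direction of bias is not given by the documents. Equal and similarly related loss causes none, and loss concentrated in the tamsulosin arm works against non-inferiority.
- The illustration is on the USI level, not on the change that will be tested.

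All of this stands, and it confines the point to missing questionnaires and to a conditional bias. It does not supply a rule for the patient without both scores. The named test cannot use that patient, and no planned analysis shows whether it matters.

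**Conclusion.** The point holds as a complete-case problem. The primary test is by randomised arm but covers only patients with both POD1 and POD7 scores, under an ITT label, in an open-label non-inferiority trial with no missing-score method and no sensitivity analysis. The completer count of 94 and the total of 100 are not reconciled.

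Bias toward non-inferiority needs loss that is both related to poor relief and higher on hyoscyamine. With 10% loss in that arm only, of patients 0.5 to 1 SD worse, one-sided type I error would go from 2.5% to between 4.3% and 7.0%, on the assumptions of CV .25 for the level, a fixed 15% margin and 47 per arm. These figures are not a forecast. The documents do not support saying that the result will be biased, or in which direction. The change is inexpensive and should be made before the data are analysed.

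**What to change.** 1. **Section 5.5, primary analysis.** Replace the complete-pair t-test with a longitudinal mixed model of the pre-stent, POD1 and POD7/removal USI scores, with arm, visit and arm-by-visit terms and unstructured within-patient covariance. Use every available score from all randomised patients who were stented, by randomised arm. Test the planned POD1-to-POD7 contrast between arms against the margin stated in 5.5. Testing POD7 alone would part the test from a margin that is defined on the change. Section 5.3 warns that some pre-stent scores may be a poor baseline, so they enter as supporting information only.
2. **One sensitivity analysis.** The mixed model assumes data are missing at random, so it does not cover loss that depends on the unseen score. Impute missing hyoscyamine scores worse by the margin, or run a tipping-point analysis. On the level scale used above, one margin is .15/.25 = 0.6 SD, so a tipping point is the better choice if larger gaps are thought credible.
3. **Post-randomisation exclusions.** Restricting to stented patients is itself an exclusion after open-label randomisation. Report by arm the numbers not stented and the numbers made screen failures, with reasons.
4. **Sections 4.3, 5.3 and 5.4.** State 94 as the evaluable target and 100 as the number randomised, with the 6% loss this implies. This settles the count; it does not by itself cure bias from missing scores.

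Cost: somewhat more analysis work and possibly a less favourable estimate. No extra data are needed.
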